2.1.2. Sub-Study B

Table 3. Sub-Study B Objectives and Endpoints

Objectives	Endpoints
Primary:	Primary:
Phase 1b	Phase 1b

 • To assess the DLT rate and estimate the MTD of sasanlimab in combination with axitinib and SEA-TGT to determine the RP2D for the combination. 	
 • DLTs during the DLT-observation period.
Phase 2	Phase 2

 • To assess the ORR of sasanlimab in combination with axitinib and SEA-TGT. 	
 • OR, defined as confirmed CR or PR, as assessed by the investigator using RECIST v1.1.
Secondary:	Secondary:
Phase 1b	Phase 1b

Objectives	Endpoints

 To assess the overall safety and tolerability of the combined investigational products. 	
 AEs graded according to the NCI-CTCAE v5.0 and changes in clinical laboratory test parameters.

 To assess the anti-tumor activity of the combined investigational products. 	
 OR, DR, TTR, PFS by investigator assessment using RECIST v1.1.

 To characterize the PK of the investigational products. 	
 PK parameters (Cmax, Ctrough) of sasanlimab, axitinib, and SEA-TGT, as data permit.

 To evaluate the immunogenicity of sasanlimab. 	
 ADA (i.e., incidence) against sasanlimab, as data permit.

 To evaluate the immunogenicity of SEA-TGT. 	
 ADA (i.e., incidence) against SEA-TGT, as data permit.
Phase 2	Phase 2

 To assess other measures of anti-tumor activity of the combined investigational products. 	
 DR, TTR, PFS by investigator assessment using RECIST v1.1, and OS.

 To assess the overall safety and tolerability of the combined investigational products. 	
 AEs graded according to the NCI-CTCAE v5.0 and changes in clinical laboratory test parameters.

 To characterize the PK of the investigational products. 	
 PK parameters (Cmax, Ctrough) of sasanlimab, axitinib, and SEA-TGT, as data permit.

 To evaluate the immunogenicity of sasanlimab. 	
 ADA against sasanlimab, as data permit.

 To evaluate the immunogenicity of SEA-TGT. 	
 ADA against SEA-TGT, as data permit.

 To assess the association between anti-tumor activity and PD-L1 expression. 	
 OR by PD-L1 expression in available tumor tissue (archival or de novo, primary or metastatic).
Exploratory	Exploratory
Phase 1b	Phase 1b

 To understand the relationship between the therapeutic interventions being studied and the biology of the participant's NSCLC. 	
 Biomarkers, consisting of DNA, RNA, protein, metabolites or defined cell types, resulting from analyses of peripheral blood and/or tumor tissue biospecimen obtained at baseline, on treatment or at end-of-study.
Phase 2	Phase 2

 To understand the relationship between the therapeutic interventions being studied and the biology of the participant's NSCLC. 	
 Biomarkers, consisting of DNA, RNA, protein, metabolites or defined cell types, resulting from analyses of peripheral blood and/or tumor tissue biospecimen obtained at baseline, on treatment or at end-of-study.

Primary Estimand(s)

Phase 1b:

Primary Estimand (DLT): DLT rate estimated based on data from DLT-evaluable participants during the DLT-evaluation period (Cycle 1 – first 21 days of study treatment) in Phase 1b.

Variable: Occurrence of DLTs.

Analysis population: DLT-evaluable participants defined as participants who receive at least 1 dose of the combination study treatment in Phase 1b and either experience DLT during the DLT-evaluation period or complete the DLT-evaluation period without DLT. Participants

without DLTs who receive less than 75% of the planned dose of each study intervention in Cycle 1 for reasons other than treatment-related toxicity are not evaluable for DLT. All participants deemed non-evaluable for DLT may be replaced.

Population-level summary measure: DLT rate defined as the number of DLT evaluable participants with DLTs in the DLT-evaluation period divided by the number of DLT-evaluable participants in the DLT-evaluation period.

Phase 2:

Primary Estimand (OR): the treatment effect of sasanlimab + axitinib + SEA-TGT assessed by the ORR, based on Investigator assessment per RECIST v1.1, in the analysis population.

- Variable: Objective response defined as confirmed CR or PR according to RECIST v1.1 based on investigator assessment. Both CR and PR must be confirmed by repeat assessments performed no less than 4 weeks after the criteria for response are first met.
- Analysis population: all participants who received at least 1 dose of study intervention without regard to tolerability or duration of treatment.
- Population-level summary measure: ORR is defined as the proportion of participants in the analysis population with an OR and 2-sided 95% CI for ORR using the Clopper-Pearson method. Participants who do not have a post-baseline tumor assessment due to early progression of disease, who receive anti-cancer therapies other than the study treatments prior to reaching a CR or PR, or who die, or have PD, or stop tumor assessments for any reason prior to reaching a CR or PR will be counted as non-responders in the assessment of OR. Each participant will have an objective response status (0: no OR; 1: OR).

[figure not shown]
2.2. Study Design

This is a prospective, open-label, multi-center, parallel group, Phase 1b/2 umbrella study to evaluate safety, efficacy, pharmacokinetics, and/or pharmacodynamics of sasanlimab in combination with targeted agents that increase anti-tumor immunity and activity in adult participants with locally advanced or metastatic NSCLC. Each sub-study may be conducted in parallel, as new agents are included to begin a sub-study within the framework of the master protocol. Each sub-study will specify the treatment setting. Participants will receive study interventions until permanent treatment discontinuation criteria are met.

The combination arms will be assessed individually in 2 parts:

1. A Phase 1b part to evaluate safety of the combination and select an RP2D dose level for the combination.
2. A Phase 2 part to evaluate the activity and further evaluate safety of the RP2D from the Phase 1b part in pre-specified participant populations.

Figure 1. Study Design Schema

2.2.1. Sub-study A Design

Phase 1b

The sasanlimab dose will remain fixed for all dosing cohorts in the Phase 1b part of Sub-Study A.

Beginning with the starting dose level, cohorts of 3-6 participants will be enrolled, treated, and monitored during the 28-day DLT evaluation period (Cycle 1). Participants without DLTs who receive less than 75% of the planned dose of each study drug in the combinations in Cycle 1 for reasons other than treatment-related toxicity are not evaluable for DLT. A minimum of 3 DLT-evaluable participants will be required; additional participants will be enrolled in the specific enrollment cohort to replace participants who are not considered DLT-evaluable, where required. When all DLT-evaluable participants treated in a given enrollment cohort have completed the DLT observation period or experienced a DLT, whichever occurs first, the posterior distribution for the risk of DLT for new participants at different dose levels for the combination of interest will be evaluated. The posterior distributions will be summarized to provide the posterior probability that the risk of DLT lies within the intervals shown below:

- Underdosing: [0, 0.16);
- Target toxicity: [0.16, 0.33);
- Excessive toxicity: [0.33, 1].

In addition to accumulating safety data and observed DLTs, decisions on further participant enrollment and dose level selection will be guided by the escalation with overdose control (EWOC) criterion. A combination dose may only be used for newly enrolled participants if the risk of excessive toxicity at that combination dose is less than 25% (0.25). Refer to Appendix 2 for further details of the BLRM.

An RP2D below the MTD, or highest safe dose tested, may be determined based on other safety, clinical activity, PK, and pharmacodynamic data. Before expanding into Phase 2, safety will be confirmed in at least 9 DLT-evaluable participants treated at the RP2D.

Table 4. Sub-Study A Combination: Sasanlimab + Encorafenib + Binimetinib – Available Dose Levels

Dose Level	Sasanlimab	Encorafenib	Binimetinib
1	300 mg SC Q4W	450 mg QD	45 mg BID
0 (starting dose)	300 mg SC Q4W	300 mg QD	45 mg BID
-1	300 mg SC Q4W	300 mg QD	30 mg BID

DLT period = 1 cycle. The treatment cycle is 28 days.

BLRM dose escalation schema will be used for the dose-finding phase of the study.

Phase 2 Design:

Phase 2 Sub-Study A will enroll approximately 62 participants with BRAF^{V600}-mutated NSCLC and will evaluate the activity and safety of sasanlimab + encorafenib + binimetinib.

2.2.2. Sub-study B Design

Phase 1b

Phase 1b will enroll participants in any line therapy for advanced NSCLC with no restrictions on the types of previous therapies, and who have any PD-L1 expression status. First, the safety of the sasanlimab and axitinib combination will be confirmed. Up to 2 dose levels of axitinib given in combination with sasanlimab CCI will be investigated (Table 5). The decision to de-escalate axitinib (from 5 mg BID to 3 mg BID) will be based on mTPI decision criteria based on the number of DLT evaluable participants and number of DLTs in those participants.

Initially 3-4 participants will be treated with sasanlimab CCI + axitinib 5 mg BID and monitored during the 21-day DLT evaluation period (Cycle 1). If the mTPI decision criteria allow escalation, then the triplet cohort may be opened. Otherwise, the doublet cohort can be expanded with an additional 3 participants enrolled or de-escalated to the lower dose (3 mg BID) per the mTPI decision criteria.

Table 5. Sub-Study B Phase 1b, Doublet Cohorts Dose Levels

Dose Level	Sasanlimab	Axitinib
------------	------------	----------

0 (Starting Dose)	CCI	5 mg BID
-1	CCI	3 mg BID

DLT period = 1 cycle of 21 days.
 mTPI dose finding schema will be used for dose finding.

After the safety of the doublet is confirmed, the triplet combination may be opened. Up to three dose levels of SEA-TGT may be investigated (Table 6) and initially 3-4 participants will be treated and monitored at the starting dose level. The enrollment of subsequent participants (dose escalation or de-escalation cohorts) will be guided by mTPI design. At least 6 participants will be treated at the RP2D of the triplet combination before proceeding to Phase 2.

Table 6. Sub-Study B, Phase 1b, Triplet Cohorts Dose Levels

Dose Level	Sasanlimab	Axitinib*	SEA-TGT**
1	CCI	3 or 5 mg BID	Single-agent RP2D IV Q3W
0 (Starting Dose)	CCI	3 or 5 mg BID	Single-agent RP2D -1 IV Q3W
-1	CCI	3 or 5 mg BID	Single-agent RP2D -2 IV Q3W

DLT period = 1 cycle of 21 days.
 mTPI dose finding schema will be used for dose finding.

*Axitinib dose will be determined by the doublet cohorts and will be fixed in the triplet cohorts.

**Final dose pending ongoing first-in-human monotherapy study exploring 0.01, 0.1, 0.3, 1, 3, and 10 mg/kg (SGNTGT-001).

A minimum of 3 DLT-evaluable participants will be required in each cohort; additional participants will be enrolled in the specific enrollment cohort to replace participants who are not considered DLT-evaluable, where required. When all DLT-evaluable participants treated in a given enrollment cohort have completed the DLT observation period or experienced a DLT, whichever occurs first, the posterior probabilities for the risk of DLT for new participants at different dose levels for the combination of interest will be evaluated. If the toxicity rate of the currently used dose level is far smaller than the target probability of toxicity (pT) of 0.30, the mTPI will recommend escalating the dose level; if it is close to pT, the mTPI will recommend continuing at the current dose; if it is far greater than pT, the mTPI will recommend de-escalating the dose level. The mTPI dose de-escalation/escalation recommendation will be based on the estimated toxicity rate and 3 intervals (underdosing, target toxicity, and excessive toxicity) as shown below:

- If current dose is in the underdosing [0, 0.25) toxicity interval: escalate to next higher dose;
- If current dose is in the target toxicity [0.25, 0.35) toxicity interval: stay at current dose;
- If current dose is in the excessive toxicity or overdosing [0.35, 1] toxicity interval: de-escalate to a lower dose

The number of participants to be enrolled in Phase 1b will depend upon the observed safety profile, which will determine the number of participants at each dose level and the number of dose levels explored.

It is anticipated that up to approximately 20 total participants will be enrolled in Phase 1b starting with Dose Level 0 of the doublet cohorts and including the triplet cohorts.

An RP2D below the MTD, or highest safe dose tested, may be determined based on other safety, clinical activity, PK, and pharmacodynamic data.

Cumulative DLT data will continue to be evaluated using the mTPI design in the Phase 2 part. Should emerging data indicate that the dose level tested in the Phase 2 expansion cohort is more toxic than previously estimated ($\geq 35\%$ DLT rate), the next lower dose level may be explored, and may be declared as the RP2D for the triplet combination.

Phase 2 Design:

Once the RP2D of the triplet is defined, the Phase 2 part of the study may be initiated. Participants will be allocated to 1 of 3 treatment arms based on lines of prior therapy and PD-L1 TPS. For participants with previously untreated NSCLC, competitor data for PDx/TIGIT doublet combinations suggest that clinical activity may be enriched in the subgroup of participants with PD-L1 TPS $\geq 50\%$ as compared to those with PD-L1 TPS 1-49%. Therefore, participants will be enrolled into 2 separate treatment arms based on PD-L1 expression to allow for estimation of clinical activity in each subgroup:

- Treatment Arm B1 (n=20): treatment-naïve participants with low PD-L1 (levels 1-49%);
- Treatment Arm B2 (n=20): treatment-naïve participants with high PD-L1 (levels $\geq 50\%$).

Given the existing data and high unmet need, a 3rd group of participants who have received prior checkpoint treatment is planned:

- Treatment Arm B3 (n=20): participants whose disease has progressed on prior PD-1/PD-L1 therapy and who have PD-L1 TPS $\geq 1\%$.

Phase 2 will enroll a total of approximately 60 participants and will evaluate the anti-tumor activity and further evaluate the safety of the triplet combination of sasanlimab + axitinib + SEA-TGT.

3. ENDPOINTS AND BASELINE VARIABLES: DEFINITIONS AND CONVENTIONS

Endpoints specific to a Sub-Study are indicated.

3.1. Primary Endpoint(s)

3.1.1. Phase 1b

DLT during the DLT-observation period is the primary safety endpoint of Phase 1b for the combination evaluated.

- For Sub-Study A the DLT-observation period is the first 28 days after and including the date of first dose (i.e. Cycle 1 Day 1 through Cycle 1 Day 28).
- For Sub-Study B the DLT-observation period is the first 21 days after and including the date of first dose (i.e., Cycle 1 Day 1 through Cycle 1 Day 21).

3.1.2. Phase 2

3.1.2.1. Sub-Study A

- Durable OR is defined as a complete response (CR) or partial response (PR) according to RECIST v1.1 from the date of first dose of study treatment until the date of the first documentation of progressive disease (PD) and lasting for at least 10 months (298 days) from the date of first documentation of the CR or PR until progression or death. Both CR and PR must be confirmed by repeat assessments performed no less than 4 weeks after the criteria for response are first met.

Participants are considered to have had a durable OR if they had response lasting for ≥ 10 months (298 days). Each participant will have a durable objective response status (0: no durable OR; 1: durable OR).

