- Analysis population: DLT-evaluable participants defined as participants who receive at least 1 dose of the combination study treatment in Phase 1b and either experience DLT during the DLT-evaluation period or complete the DLT-evaluation

period without DLT. Participants without DLTs who receive less than 75% of the planned dose of each study drug in Cycle 1 for reasons other than treatment-related toxicity are not evaluable for DLT. All participants deemed non-evaluable for DLT may be replaced.

- Population-level summary measure: DLT rate defined as the number of DLT-evaluable participants with DLTs in the DLT-evaluation period divided by the number of DLT-evaluable participants in the DLT-evaluation period.

Phase 2:

Primary Estimand (Durable OR): the treatment effect of sasanlimab + encorafenib + binimetinib assessed by the Durable ORR, based on Investigator assessment per RECIST v1.1, in the analysis population.

- Variable: Durable objective response defined as confirmed CR or PR according to RECIST v1.1 based on investigator assessment, lasting for at least 10 months from the date of first CR or PR until the date of the first documentation of PD, death, or start of new anticancer therapy. Both CR and PR must be confirmed by repeat assessments performed no less than 4 weeks after the criteria for response are first met.
- Analysis population: all participants who received at least 1 dose of study drug without regard to tolerability or duration of treatment.
- Population-level summary measure: Durable ORR defined as the proportion of participants in the analysis population with durable OR and 2-sided 95% CI for durable ORR using the Clopper-Pearson method. Participants who do not have a postbaseline tumor assessment due to early progression of disease, who receive anticancer therapies other than the study treatments prior to reaching a CR or PR for 10 months, or who die, have PD, or stop tumor assessments for any reason prior to reaching a CR or PR for 10 months will be counted as non-responders in the assessment of durable OR. Each participant will have a durable objective response status (0: no durable OR; 1: durable OR).

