5.2.8. Standard derivations and reporting conventions

The following conversion factors will be used to convert days into weeks, months or years: 1 week = 7 days, 1 month = 30.4375 days, 1 year = 365.25 days.

Demographics and physical measurements:

Age [years]: (year of given informed consent - year of birth)

The integer part of the calculated age will be used for reporting purposes.

For reporting conventions, mean and median should generally be displayed one more decimal place than the raw data and standard deviation should be displayed to two more decimal places than the raw data. Percentages will be reported to one decimal place. The rounding will be performed to closest integer / first decimal using the common mid-point between the two consecutive values. E.g., 5.1 to 5.4 will be rounded to an integer of 5, and 5.5 to 5.9 will be rounded to an integer of 6.

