6.1.2.1. Sub-Study A - Durable Objective Response

6.1.2.1.1. Primary analysis

Durable ORR is calculated as the proportion of participants in the full analysis population with durable OR along with a 2-sided 95% CI for durable ORR using the Clopper-Pearson method. Participants who do not have a post-baseline tumor assessment due to early progression of disease, who receive anti-cancer therapies other than the study treatments prior to reaching a CR or PR for 10 months, or who die, have PD, or stop tumor assessments for any reason prior to reaching a CR or PR for 10 months will be counted as non-responders in the assessment of Durable OR. Each participant will have a durable objective response status (0: no durable OR; 1: durable OR).

Refer to Section 6.2.2 for assessment of response.

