6.2.2.3. Duration of response

Duration of Response (DR) is defined, for participants with OR, as the time from the first documentation of objective response (CR or PR) to the date of first documentation of PD or death due to any cause. If a participant has not had an event (PD or death), DR is censored at the date of last adequate tumor assessment. The censoring rules for DR are described in Table 9.

$$\text{DR (months)} = [\text{date of event or censoring} - \text{first date of OR} + 1] / 30.4375$$

Table 9. Outcome and Event Dates for DR Analyses

Scenario	Date of event/censoring	Outcome
PD or death - After at most one missing or inadequate post-baseline tumor assessment, OR - ≤ 16 weeks after the date of first dose of study treatment	Date of PD or death	Event
PD or death - After 2 or more missing or inadequate post-baseline tumor assessments	Date of last adequate tumor assessment ^a documenting no PD before new anti-cancer therapy is given or missed tumor assessments	Censored
No PD and no death	Date of last adequate tumor assessment ^a documenting no PD before new anti-cancer therapy is given or missed tumor assessments	Censored
Treatment discontinuation due to ‘Disease progression’ without documented progression	Not applicable	Information is ignored. Outcome is derived based on documented progression only.
New anti-cancer therapy given	Date of last adequate tumor assessment ^a documenting no PD before new anti-cancer therapy is given or missed tumor assessments	Censored

^a If there are no adequate post-baseline assessments prior to PD or death, then the time without adequate assessment should be measured from the date of first dose of study treatment; if the criteria were met the censoring will be on the date of first dose of study treatment.

Kaplan-Meier estimates (product-limit estimates) will be presented by treatment group together with a summary of associated statistics including the median DR time with 2-sided 95% CIs. In particular, the DR rates at 6, 10, 12, 15, 18, and 24 months will be estimated with corresponding 2-sided 95% CIs. The CIs for the median will be calculated according to Brookmeyer and Crowley (1982)² and the CIs for the survival function estimates at the time points defined above will be derived using the log-log transformation according to Kalbfleisch and Prentice (2002)⁶ (conftype=loglog default option in SAS Proc LIFETEST)

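### The durable-response threshold of 298 days is 9.8 months, not 10, by the SAP's own conversion, and the SAP leaves open how durable response treats progression or death after missed scans

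*SAP*

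**What the plan says.** **Threshold.** Section 3.1.2.1 of the SAP defines durable objective response as a confirmed CR or PR "lasting for at least 10 months (298 days) from the date of first documentation of the CR or PR until progression or death", and repeats the equation of 10 months with 298 days in its next paragraph. The primary estimand in Section 2.1.1 gives no day count: the response is one "lasting for at least 10 months from the date of first CR or PR until the date of the first documentation of PD" (or death or new therapy). The primary analysis in Section 6.1.2.1.1 also speaks only of 10 months.

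**Conversion.** Section 5.2.8 fixes "1 week = 7 days, 1 month = 30.4375 days, 1 year = 365.25 days". Section 6.2.2.3 computes DR in months as the event or censoring date minus the first response date, plus 1, divided by 30.4375. It adds that "the DR rates at 6, 10, 12, 15, 18, and 24 months will be estimated".

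**Missed scans.** For DR, Table 9 has a row for progression or death "After 2 or more missing or inadequate post-baseline tumor assessments"; the outcome is censoring at the last adequate assessment before the gap. For durable response, Section 6.1.2.1.1 says that participants who die, progress or "stop tumor assessments for any reason prior to reaching a CR or PR for 10 months will be counted as non-responders". It does not mention participants who miss scans and then resume. It closes with "Refer to Section 6.2.2 for assessment of response", and Table 9 lies within Section 6.2.2.

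**The concern.** The primary test for Sub-Study A counts participants whose durable status is 1 and rejects the null at 30 or more of 62 (Section 5.1.2.1). Each participant's 0/1 status should therefore follow from the text without judgement. Two things stand in the way.

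First, the SAP carries two thresholds for one endpoint: 298 days in Section 3.1.2.1, and 10 months, which its own conversion makes more than 304 days. The shorter one can only add durable responders.

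Second, no rule says what happens when two or more assessments are missed, scanning resumes and progression is then found, or the participant dies after the gap. Two programmers could score the same participant differently on the primary endpoint. In a single-arm trial assessed by the investigator, the more generous choice moves the result towards success.

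**Working it through.** **1. The day count.** Inputs: 298 days (Section 3.1.2.1); 30.4375 days per month (Section 5.2.8); the +1 in the DR formula (Section 6.2.2.3).

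- 10 × 30.4375 = 304.375 days, so 298 is 6.4 days short.
- 298 / 30.4375 = 9.79 months. If 298 is a date difference, the DR formula gives (298 + 1) / 30.4375 = 9.82 months.
- Other conventions do not give 298: 28-day months give 280, 30-day months 300, 365/12 gives 304.2, and calendar months 303 to 306. Only 305 − 7 = 298 fits, and the SAP states no 7-day window for this endpoint.

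**2. Who is affected.** Take 298 as a date difference between first response and progression or death:

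| Date difference (days) | Status by 298-day rule | DR (months) |
|---|---|---|
| 298 | durable | 299/30.4375 = 9.82 |
| 303 | durable | 304/30.4375 = 9.99 |
| 304 | durable | 305/30.4375 = 10.02 |

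Events at 298 to 303 days are durable for the primary endpoint but fall before month 10 in the DR analysis.

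Section 6.2.2.5 puts the second planned assessment at 16 weeks, which implies scans about every 8 weeks. Scan-to-scan intervals near the threshold are then 280 and 336 days. With an assumed ±7 days at each scan they span 266–294 and 322–350 days, and neither range reaches 298–303. So it is mainly deaths and off-schedule scans that fall in the gap.

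**3. Effect on the test.** The rule of 30 or more of 62 at a null rate of 35% has exact one-sided alpha P(X ≥ 30 | 62, 0.35) = 0.0205. Suppose the true 10-month durable rate is 0.35 and DR is exponential. The rate at 298 days is then p = 0.35 × (ORR/0.35)^(6.375/304.375). The ORR range is an assumption.

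| Assumed ORR | Rate at 298 days | P(X ≥ 30) |
|---|---|---|
| 48% | 0.3523 | 0.0225 |
| 60% | 0.3540 | 0.0240 |
| 70% | 0.3551 | 0.0251 |

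This model spreads events evenly over time. Scheduled scans would put fewer progressions in the six-day gap.

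**4. The missed-scan case.** Assume 8-weekly scans, a first response at week 8 (confirmed later), a last adequate scan at week 32, weeks 40 and 48 missed, and progression at week 56.

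- Literal reading of Section 3.1.2.1: (56 − 8) × 7 = 336 days until progression, so durable.
- Table 9: censored at week 32. (32 − 8) × 7 = 168 days, and (168 + 1) / 30.4375 = 5.6 months.

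The documents give no frequency for such gaps, so their effect on the test cannot be estimated. Purely as an illustration, if they added one or two expected durable responders in 62, P(X ≥ 30) would be 0.038 or 0.066.

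**The case against.** **298 may be deliberate.** 305 less a 7-day window is exactly 298, and a window may be described in the protocol, which is not at hand. That stands as a possible explanation, and the fix allows for it. It does not remove the contradiction, because the SAP presents 298 days as the equivalent of 10 months and uses a different equivalent for DR.

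**The missed-scan rule may already be covered.** The clause on stopping assessments, the cross-reference to Section 6.2.2, and Section 5.2.6, which ties the new-therapy date to censoring in both Sections 6.1.2 and 6.2.2, can be read as making such a participant a non-responder. A reader might infer the opposite from the literal wording, namely that the SAP counts these participants as durable. The documents do not support that: it is an inference from silence. What stands is that the rule is unspecified.

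**Durable ORR and DR differ by design.** One is a proportion of all treated participants with dropouts as failures; the other is a Kaplan-Meier estimate in responders with censoring. Disagreement between them is not in itself an error, and Table 9 censors rather than scores anyone as not durable. This is correct. The defect is narrower: the meaning of 10 months differs between the two, and the status of the missed-scan case is open.

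**The size can be overstated.** A reader might reason that one wrongly scored participant amounts to a cut-off of 29, with exact alpha 0.037. That would require such a participant in every trial, which nothing in the SAP suggests.

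**Conclusion.** The day count is wrong as written: by the SAP's own conversion 298 days is 9.79 months (9.82 with the +1), and nothing in the SAP explains the difference. Its effect is small but in the direction of success. Rejection probability at the null goes from 0.0205 to about 0.0225–0.0251, assuming exponential DR, a true 10-month durable rate of 35% and overall response of 48–70%. With scans about every 8 weeks, which is inferred, mainly deaths and off-schedule scans are affected.

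The missed-assessment point is an omission in the primary endpoint. The literal wording permits a durable score where Table 9 censors DR far earlier, and other passages can be read against it. No reliable size can be put on it. Both points should be settled before the primary analysis, since each decides a 0/1 status that enters an exact count.

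**What to change.** 1. In Section 3.1.2.1, define durable response as a confirmed response with DR of at least 10.0 months by the Section 6.2.2.3 formula. State the counting convention: 305 days counted inclusively, which is a date difference of at least 304 days. Writing 305 without the convention would risk an off-by-one error. If 298 reflects a visit window, say so and reconcile it with the DR analysis and its 10-month rate.
2. In Section 6.1.2.1.1, add that participants whose progression or death follows two or more missing or inadequate assessments before month 10 are scored as not durable. This is consistent with how that section already treats stopped assessments. It is a scoring rule for durable response, to be stated as such and not attributed to Table 9, which only censors.

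The cost is two sentences and one programming constant, with a possibly slightly lower observed durable ORR. Section 2 of the SAP says major modifications of the primary endpoint definition are also made by protocol amendment, so one is needed only if the sponsor regards this as major.
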